- E Every 2 cycles (+/- 7 days) from baseline scan while receiving cobimetinib and vemurafenib. Patients who are noted to have PR or CR should have a confirmation scan performed 4-8 weeks (+/- 7 days) after the scan demonstrating response. Once patients on Cohort A complete treatment, staging scans must be performed every 16 weeks (+/- 4 weeks) (from last scan performed during treatment) until they have reached 2 years post-registration or until documented progression. Patients on Cohort B who receive surgery or radiation at investigator discretion must submit initial post-operative/post-RT scan, 1 year (+/- 14 days) post-op/post-RT scan and any other scans done as part of clinical care after surgery and radiation. Of note, surgery can be delayed by not more than 4 weeks to obtain a confirmatory scan to document a response. Patients discontinuing for reasons other than progressive disease will have staging scans every 16 weeks (+/- 4 weeks) until they have reached 2 years post-registration or until documented progression, whichever comes first.

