### 11.3.3 Measurement at follow-up evaluation:

- A subsequent scan must be obtained 4 weeks following initial documentation of an objective status of either complete response (CR) or partial response (PR) for confirmation of response.
- In the case of stable disease (SD), follow-up measurements must have met the SD criteria at least once after study entry at a minimum interval of 8 weeks (see [Section 11.4.5](#)).

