##### 11.4.5.2 Evaluation of measurable lesions for local radiology review

- **Complete response (CR):** All of the following must be true:  
Disappearance of all measureable lesions on consecutive MRI or CT 4 weeks apart. No new lesions. No evidence of non-measurable disease. Lesions must be assessed using the same techniques at baseline. If [Appendix II](#) is not followed, imaging should continue per baseline acquisition parameters. Neurologically/clinically stable or improved. No corticosteroids for vasogenic edema.
- **Partial response (PR):**  
≥ 50% decrease under baseline in the sum of products of perpendicular diameters all enhancing, necrotic and cystic measurable components. No progression of nonmeasurable disease. No new lesions. All measurable and non-measurable lesions and sites must be assessed using the same techniques as baseline. If [Appendix II](#) is not followed, imaging should continue per baseline acquisition parameters. Neurologically/clinically stable or improved. Stable or reduced corticosteroid dose for vasogenic edema.
- **Progression (PD):** At least one of the following must be true:  
> 25% increase in the sum of products of all measurable lesion components (including enhancing, necrotic and cystic components) over smallest sum observed (over baseline if no decrease) using the same techniques as baseline. OR clear worsening of any nonmeasurable disease, OR appearance of any new lesion/site, OR clear clinical worsening or failure to return for evaluation due to death or deteriorating condition (unless clearly unrelated to this cancer)  
>25% increase in the sum of products of all measurable lesion components (including enhancing, necrotic and cystic components) but < 50% increase in the sum of products of all measurable lesion components (including enhancing, necrotic and cystic components) AND no new lesions/sites in scans obtained AND no clear clinical deterioration: When all of these conditions are met, the patient may continue on drug for 4 weeks. Imaging must be repeated 4 weeks later

(+/- 7 days). If imaging at 4 weeks shows continued growth of greater than 25%, then patient has definitive progression and date of progression should be back dated to the first MRI where there was a >25% increase.

- **Stable disease (SD):** Neither sufficient shrinkage to qualify for PR, nor sufficient increase to qualify for PD taking as reference the MSD. Stable clinically

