#### 11.4.5.4 Evaluation of measurable lesions for central radiology review

Criteria for central radiology review is based on volumetric criteria that has been used in other brain tumors, including benign brain tumors.

- **Complete response (CR):** All of the following must be true:  
Disappearance of all measurable lesions on consecutive magnetic resonance imaging (MRI) or CT 4 weeks apart. No new lesions. No evidence of non-measurable disease. Lesions must be assessed using the same techniques at baseline. Neurologically/clinically stable or improved
- **Partial response (PR):**  
≥20% decrease under baseline in the volume of all measurable lesions. No progression of nonmeasurable disease. No new lesions. All measurable and non-measurable lesions and sites must be assessed using the same techniques as baseline. Neurologically/clinically stable or improved
- **Progression (PD):** At least one of the following must be true:  
> 20% increase in the volume of all measurable lesions using the same techniques as baseline, OR clear worsening of any nonmeasurable disease, OR appearance of any new lesion/site, OR clear clinical worsening or failure to return for evaluation due to death or deteriorating condition (unless clearly unrelated to this cancer)
- **Stable disease (SD):** Neither sufficient shrinkage to qualify for PR, nor sufficient increase to qualify for PD. Stable clinically

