### 13.2 Statistical design and analysis for the primary endpoint

#### 13.2.1 Primary endpoints

The primary end point is response rate (RR), defined as the number of responses achieved during treatment with BRAF and MEK inhibitors divided by the total number of evaluable patients. For the recurrent cohort, only responses achieved during the first four cycles of treatment with BRAF and MEK inhibitors will count toward the primary endpoint. A patient will be deemed to have a response if CR or PR measured by central radiologic review (see [Section 11.4.5.4](#) and [11.4.5.5](#)) is achieved. Contrast-enhanced magnetic resonance imaging (MRI) or CT will be performed every 2 cycles with volumetric assessment.

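### The plan requires a scan to confirm a partial response but does not say whether the primary endpoint uses it, so a single 20% volume reading can count as a response

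*Combined protocol and SAP*

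**What the plan says.** **Primary endpoint (13.2.1).** "A patient will be deemed to have a response if CR or PR measured by central radiologic review" is achieved, with reference to 11.4.5.4 and 11.4.5.5. Objectives 2.1.1 and 2.1.2 take the best response over the first four cycles. Imaging is every 2 cycles, so there are two scheduled chances to respond.

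**Central criteria (11.4.5.4).** CR carries its own repeat: "Disappearance of all measurable lesions on consecutive magnetic resonance imaging (MRI) or CT 4 weeks apart". PR does not. Its size condition is "≥20% decrease under baseline in the volume of all measurable lesions", beside conditions on new lesions, non-measurable disease and clinical status.

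**Confirmation.** Section 11.3.3: "A subsequent scan must be obtained 4 weeks following initial documentation of an objective status of either complete response (CR) or partial response (PR"), the stated purpose being confirmation. Section 5.0, footnote E: "Patients who are noted to have PR or CR should have a confirmation scan performed 4-8 weeks (+/- 7 days) after the scan demonstrating response". Footnote E also lets surgery wait up to 4 weeks for such a scan.

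**Who reads when.** Central review is retrospective (6.3.1). Sites manage patients on bidimensional area (11.0), where PR is "≥ 50% decrease under baseline in the sum of products of perpendicular diameters" (11.4.5.2). Real-time central review is only a contingency, prompted by discordant progression (13.5.3).

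**Decision rule (13.2.2, 13.2.3).** In each cohort, stop if there are 0 responses in 9; declare activity with at least 3 in 16. The stated one-sided error is 0.041 at a 5% rate and the power 0.886 at 30%.

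**The concern.** Two analysts could follow this plan and count different responders. One would take 11.4.5.4 literally and accept a single 20% reading as PR; the other would apply 11.3.3 and require the second scan. With a cut-off of 3 in 16, one patient can decide a cohort.

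The second scan may also be missing where it matters. Footnote E does not name the reader whose PR prompts it. Because central review comes later, the prompt is in practice probably the local reading, and local PR is a far larger shrinkage than central PR. A moderate volume loss can therefore be a primary-endpoint response while the site records stable disease and orders no extra scan.

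At stake is how far the operating characteristics depend on measurement precision. A 20% threshold read once, with two chances to cross it, is more exposed to measurement error than a threshold that must be crossed twice.

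**Working it through.** **1. The plan's own figures.** For response probability p,

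P(declare active) = Σ over x = 1..9 of Bin(x; 9, p) × P(Y ≥ max(0, 3 − x)), with Y ~ Bin(7, p).

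This gives 0.0406 at p = 0.05 and 0.8864 at p = 0.30, against 0.041 and 0.886 stated. Stopping at stage 1 under the null is 0.95^9 = 0.630, as stated. The design arithmetic is correct; the question is what enters it as a response.

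**2. Local and central PR on one scale.** For isotropic shrinkage, volume scales as area^1.5.
- A 50% area decrease is 1 − 0.5^1.5 = 64.6% of volume.
- A 20% volume decrease is 1 − 0.8^(2/3) = 13.8% of area.

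Volume losses of roughly 20–65% are thus central PR but not local PR. The conversion is approximate: local area sums separately measured enhancing and cystic components, so mixed tumors need not follow it.

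**3. Which patients lack a second scan.**
- First central PR at Cycle 2: the scheduled Cycle-4 scan is 8 weeks later, inside footnote E's window.
- First central PR at Cycle 4, drug continued (allowed in Cohort B by 7.1.2, and in Cohort A with approval by 7.1.1): rescanned every 2 cycles.
- First central PR at Cycle 4, locally stable, drug stopped: no scheduled on-treatment repeat. In Cohort A, surgery or radiation follows (7.1.1) and scheduled scans are then 16 weeks (± 4 weeks) apart. This is the gap.

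**4. Size under an assumed error.** The documents give no measurement error, so the CV is an assumption shown as a range. Model: no true change; independent log-normal error on each scan; one baseline shared by two on-treatment scans; PR if the volume ratio is at most 0.80. Then

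sd = √ln(1 + CV²); z = ln(0.8) / (sd·√2); one scan = Φ(z); both = Φ₂(z, z; ρ = 0.5); either = 2Φ(z) − both.

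At CV 10%: sd = 0.0998, z = −1.582, one scan 0.057, both 0.0146, either 0.099.

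Three counting rules follow:
- No PR is confirmed: either scan suffices.
- Only first-at-Cycle-4 PRs go unconfirmed: a Cycle-2 PR must recur at Cycle 4, so the Cycle-4 reading alone decides (one scan).
- Both scans must agree.

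Each cell gives the false-PR probability per patient, then P(declare active) from the rule in step 1.

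| CV | No PR confirmed | Only first-at-Cycle-4 unconfirmed | Both scans agree |
|---|---|---|---|
| 5% | 0.2%; about 0 | 0.1%; about 0 | below 0.01%; below 0.001 |
| 8% | 4.4%; 0.03 | 2.4%; 0.006 | 0.4%; below 0.001 |
| 10% | 9.9%; 0.20 | 5.7%; 0.056 | 1.5%; 0.001 |
| 12% | 15.8%; 0.45 | 9.3%; 0.17 | 2.9%; 0.010 |

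**5. Dependence on what the 5% null means.** If 5% is the observed rate with false PRs included, the error stays 0.041. If instead 5% are genuine responders and false PRs arise among the other 95% (p = 0.05 + 0.95f), CV 10% gives 0.395, 0.217 and 0.074 for the three rules. The documents give no rationale for the 5%.

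**6. Price of confirmation.** If 5%, 10% or 20% of true responses fail to confirm, 0.30 becomes 0.285, 0.27 or 0.24, and power becomes 0.861, 0.831 or 0.758.

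**The case against.** The strongest reply is that 13.2.1 is silent, not contrary. It refers to Section 11, and 11.3.3 does not limit confirmation to local review, so a reader could say confirmation already applies. Taken the other way, best response over four cycles is a usual endpoint for a signal-finding phase 2 trial, and requiring confirmation is partly preference. Both readings are tenable, and that is why the text must choose.

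Other parts of the reply stand:
- The local trigger is inferred from retrospective central review. Footnote E names no reader.
- The gap is narrow: Cycle-2 responses are rechecked and continuing patients are rescanned. Some who stop may also have a usable scan, through the permitted surgical delay or the recent pre-irradiation scan in 7.2.1.
- The plan limits measurement error by requiring the same technique as baseline (11.4.5.4), the same pulse sequence (11.3.2) and 3D isotropic acquisition (Appendix II). At CV 5% the issue disappears.
- If responses resemble the 85% volume reduction in the case cited in 1.3, few will lie near 20%. Confirmation would then rarely change the count, though it would also cost little power.

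**Conclusion.** The gap is real and should be fixed: the plan calls for confirmation scans, builds confirmation into central CR, leaves it out of central PR, and never classifies an unconfirmed central PR. The patients exposed are those with a first central PR of roughly 20–65% volume loss at Cycle 4 who then stop drug, mainly in Cohort A.

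The size is conditional. Under the no-change model, the rule closest to the protocol's schedule (only first-at-Cycle-4 PRs unconfirmed) stays below 0.041 at CV 8% and reaches 0.056 at 10% and 0.17 at 12%.

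A reader might infer more, and the documents do not support it:
- That the trial's type I error is 0.20 or 0.45. Those figures need a CV of 10% or 12%, which the documents do not give, and no confirmation of any PR, although Cycle-2 PRs are rechecked.
- That the plan chose to count unconfirmed PRs, or that it states a local trigger. The first is silence and the second is inference.
- That the stated 0.041 is wrong. It is correct for a 5% rate, and it stands if that rate allows for false PRs.

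**What to change.** In 11.4.5.4 and 13.2.1:
1. Count a central PR as a primary response only when central review sees it again on a later scan at least 4 weeks after the first. The scheduled Cycle-4 scan serves for a Cycle-2 PR.
2. State how a central PR with no second scan is classified.
3. Report unconfirmed best response as a sensitivity analysis.

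Reconcile 11.3.3 (4 weeks) with footnote E (4–8 weeks), and state which reading triggers the confirmation scan. Its timing must also be reconciled with the passages on definitive therapy in 7.1.1 and footnote E, and with the condition in 13.2.1 that a response occur on treatment. How that is settled is a clinical matter, and no rule is proposed here.

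The cost is wording in these sections and some power: from 0.886 at a 30% rate to about 0.86, 0.83 or 0.76 if 5%, 10% or 20% of true responses fail to confirm. Those non-confirmation rates are assumptions. Any further scans or waiting depend on how the trigger and timing are reconciled.

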#### 13.2.2 Statistical design

Simon's two-stage design with one interim analysis for futility will be applied to evaluate RR within each cohort. The decision rules are included in [Section 13.2.3](#). Each cohort will require 16 evaluable patients. For the entire study, a total of 32 evaluable patients are required. Within each cohort, a total of 16 evaluable patients provides 89% power to detect a true response rate of at least 30%, with a one-sided significance level of 0.041 against the null hypothesis of 5% response rate. The overall family-wised type I error rate is 0.08. The following table shows the study characteristics of the design within each cohort:

If the true success proportion is ...	0.05	0.10	0.15	0.20	0.25	0.30
then the probability of declaring that the regimen warrants further studies is ...	0.041	0.201	0.422	0.628	0.785	0.886
and the probability of stopping at stage 1 is ...	0.630	0.387	0.232	0.134	0.075	0.040

#### 13.2.3 Analysis plan

Within each cohort, the interim and final efficacy analyses will be conducted after the 9th and 16th enrolled evaluable patient, respectively, is off treatment:

- **Interim analysis decision rules:** If there is at least one response observed, then the accrual will be continued to full accrual. Otherwise, the accrual will be terminated and conclude that the regimen does not warrant for further investigation.
- **Final analysis decision rule:** At the end of this trial, it will be concluded that the regimen warrants further investigation if at least 3 responses are observed.

In addition, point estimates will be generated for response rates within each cohort with corresponding 95% binomial confidence intervals (Duffy and Santner). There will be no formal comparison of rates among two cohorts

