## 12.0 END OF TREATMENT/INTERVENTION

### 12.1 Duration of treatment

**12.1.1 CR, PR, or SD:** Patients who are in CR, PR or SD will continue on therapy as outlined below:

- Cohort A: Patients can continue on therapy for a total of 4 cycles in cohort A, and then go on to receive radiation, surgery or both as outlined in [Section 7.1.1](#). In special circumstances, continuation of therapy with vemurafenib and cobimetinib may be granted, but only with approval from the radiation oncology chair (see [Section 7.1.1](#) for additional details). If continuation is approved, then therapy with cobimetinib and vemurafenib can continue until documented progression, unacceptable adverse events, or drug hold >28 days.
- Cohort B: Patients can continue therapy with cobimetinib and vemurafenib until documented progression, unacceptable adverse events, or drug hold >28 days (see [Section 7.1.2](#)). After treatment is completed or discontinued, patients will be followed per the study calendar in [Section 5.0](#).

**12.1.2 Disease progression:** Remove from protocol therapy any patient with disease progression. Document details, including tumor measurements, on data forms.

After disease progression, patients should be followed for survival per the study calendar ([Section 5.0](#)).

**12.1.3 Discontinuation of study agent:** If the patient discontinues protocol therapy due to reasons other than PD (i.e. for unacceptable adverse events, drug hold >28 days), prior to the completion of planned therapy as per [Section 7.0](#), patients should go on to clinical and survival follow up per the study calendar ([Section 5.0](#)). This includes:

- Patients who discontinue treatment before the end of 4 cycles of treatment to begin alternative therapy.
- Patients who discontinue continued treatment with vemurafenib and cobimetinib to begin alternative therapy (i.e. patients on Cohorts A or B who choose to continue therapy with vemurafenib and cobimetinib post the initial 4 cycles).

**12.1.4 Discontinuation of study agent in patients with expected AEs:** See [Section 8.2.4](#) for more information.

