## 13.0 STATISTICAL CONSIDERATIONS

### 13.1 Study design

This is a prospective, single-arm phase 2 study evaluating the efficacy of BRAF and MEK inhibitor combination in patients with papillary craniopharyngiomas. The primary endpoint of response rate (RR) while being treated with BRAF and MEK inhibitors will be evaluated in two cohorts, separately, i.e., newly diagnosed patients (untreated cohort) and patients who have progressed after prior radiation treatment with or without surgical resection (recurrent cohort). The statistical design is the same for each cohort. Simon's two-stage design with one interim analysis for futility will be applied to evaluate RR within each cohort. The accrual will not be halted at the interim analysis unless the accrual is too rapid.

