#### 13.3.3 Primary endpoint completion date for clinicaltrials.gov reporting

For purpose of ClinicalTrial.gov reporting, the Primary Endpoint Completion Date (PECD) for this study is the time the last patient registered has been followed for at least six months after being taken off the study treatment.

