### **13.5.2 Accrual monitoring stopping rule**

The study design assumes that 1-2 patients will accrue per month to each cohort, leading to a 1 to 2 year total accrual period (including leading time for sites to open the studies). At 12 months, if the total accrual is below 25% of the expected (fewer than 8 patients) the study team will evaluate with the scientific question will be of interest at the completion of the accrual period. If it is deemed that the scientific question is likely not to have relevance at the end of the projected accrual period, the study may close. Otherwise, the study team will continue to boost the accrual rates. The accrual rate will be checked every subsequent 6 months and the likelihood that the study questions will still be of interest at the end of the trial will be evaluated and based on this, a decision will be made whether or not to continue accrual to the study.

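### In Cohort B the futility look waits for patients to come off a treatment with no cycle limit, so it may fall after the cohort is fully enrolled

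*Combined protocol and SAP*

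**What the plan says.** - **Trigger (13.2.3).** Within each cohort the interim and final analyses follow the 9th and 16th "enrolled evaluable patient, respectively, is off treatment". The text does not say whether only the 9th patient or all of the first nine must be off drug.
- **Interim rule (13.2.3).** "If there is at least one response observed, then the accrual will be continued to full accrual"; with no response, accrual is terminated.
- **Final rule (13.2.3).** "it will be concluded that the regimen warrants further investigation if at least 3 responses are observed".
- **Endpoint window (13.2.1).** For the recurrent cohort, a response counts only if it occurs within the first four cycles. Section 7.1 sets the cycle at 28 days.
- **Time on drug (12.1.1).** "Cohort B: Patients can continue therapy with cobimetinib and vemurafenib until documented progression, unacceptable adverse events, or drug hold >28 days". Section 7.1.2 lists continued drug as one option after Cycle 4. No maximum number of cycles is given.
- **Accrual around the look (13.1).** "The accrual will not be halted at the interim analysis unless the accrual is too rapid". *Too rapid* is not defined.
- **Accrual pace.** Section 13.5.2: "The study design assumes that 1-2 patients will accrue per month to each cohort". Section 13.3.2 instead plans 16 evaluable patients per cohort over about 2 to 4 years, and says little is known about the rate.
- **End of treatment (5.0).** A calendar footnote on the post-treatment visit equates end of treatment with either four to five cycles or the end of the two drugs.

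**The concern.** The Cohort B primary endpoint is settled for each patient by the end of Cycle 4. The analysis trigger is a different event, the end of dosing, which may come much later and has no upper limit. Accrual continues by default in the meantime.

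The interim look has one purpose: to stop enrolment if the regimen is inactive. If the look arrives after the 16th evaluable patient is enrolled, the rule says to terminate accrual when none is left, and the saving implied by the stopping probabilities in 13.2.2 is lost. The final analysis of Cohort B can be held up in the same way after its data are complete, although that has no effect on accrual.

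**Working it through.** **1. The plan's own figures.** Inputs from 13.2.2 and 13.2.3: n1 = 9, stop at 0 responses; n = 16, success at 3 or more; null 5%, alternative 30%.

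- Stop at stage 1: (1 − p)^9. At 5%: 0.95^9 = 0.630. At 30%: 0.70^9 = 0.040. Both match the table.
- Declare success: sum over x ≥ 1 of P(X1 = x) × P(X2 ≥ 3 − x), with X1 from 9 patients and X2 from 7. At 5%: 0.2985 × 0.0444 + 0.0629 × 0.3017 + 0.0084 = 0.041. At 30%: 0.886. Both match.
- Expected N at 5%: 9 + (1 − 0.630) × 7 = 11.6.

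**2. When the endpoint is known.** Four cycles = 112 days = 112/30.44 = 3.7 months from the start of treatment.

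**3. When the cohort is full.** Seven evaluable patients follow the 9th; the time to enrol them is 7 divided by the monthly rate.

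| Rate per cohort | Source | 9th to 16th patient | In 28-day cycles |
|---|---|---|---|
| 2 per month | 13.5.2 | 7/2 = 3.5 months | 3.8 |
| 1 per month | 13.5.2 | 7/1 = 7.0 months | 7.6 |
| 16 in 24 months (0.67) | 13.3.2 | 7/0.67 = 10.5 months | 11.4 |
| 16 in 48 months (0.33) | 13.3.2 | 7/0.33 = 21.0 months | 22.8 |

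If the 9th patient stays on drug longer than the figure shown, the look follows full accrual. If all nine must be off drug, any one of them can cause this.

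**4. How likely that is.** The documents give no time on drug for this disease, so this is an illustration only. Assume exponential time on drug with a median of 6 to 24 months, random arrivals, and no link between response and time on drug. If only the 9th patient must be off drug, the simulated chance of a late look is 68–91% at 2 per month, 46–82% at 1, 33–74% at 0.67 and 13–56% at 0.33. If all nine must be, it runs from 34% to about 100% over the same rates.

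**5. What is lost.** With a late look, enrolment under the null is 16 instead of an expected 11.6: 7 patients in a trial that should have stopped, 0.630 × 7 = 4.4 on average. Applying the 0-of-9 rule late leaves alpha at 0.041 and power at 0.886. Dropping the rule altogether gives 0.043 and 0.901.

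**6. What a Cycle 4 trigger recovers.** The 11.6 supposes that nobody is enrolled while the first nine are assessed. With accrual running for 3.7 months after the 9th patient, about 3.7, 2.5 and 1.2 more enrol at 1, 0.67 and 0.33 per month. The average saving under the null is then 0.630 × (7 − 3.7) = 2.1, 0.630 × (7 − 2.5) = 2.8 and 0.630 × (7 − 1.2) = 3.7 patients. At 2 per month 3.7 months exceeds 3.5, so without a pause nothing is saved. A pending confirmation scan (4 to 8 weeks, plus a 7-day window, in 5.0) would move the look to 4.6–5.7 months, still before 7.0.

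**The case against.** **A bounded reading exists.** Under the calendar footnote, *off treatment* could mean four to five cycles, and 7.1.2 describes four cycles of study therapy before further treatment at the physician's discretion. On that reading most of the problem disappears. But the footnote schedules the post-treatment visit, it offers the end of drug as an alternative, and 13.2.3 does not refer to it. The ambiguity remains.

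**Harm needs a particular combination.** The look changes accrual only at 0 of 9, so responders who stay on drug cost nothing. The delay must come from a non-responding patient who remains stable, and who is the 9th (or one of the nine, if all must be off drug). Cohort B patients enter with progressive disease (3.3.2), and those who progress leave treatment (12.1.2). This limits how often the problem arises. It does not rule it out, because 12.1.1 expressly lets stable patients continue.

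**A brake on accrual exists.** A reader might infer that accrual can never be paused for the look. Section 13.1 does allow it when accrual is too rapid. Without a definition, nobody can say when that applies.

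**The fast end of the range is about pace.** At 2 per month a look at the end of Cycle 4 is already late, so that case reflects accrual speed rather than open-ended dosing. This stands, and it is why a new trigger alone is not enough.

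**Conclusion.** The point holds as a possibility that the text leaves open. Followed literally, 13.2.3 with 12.1.1 allows the Cohort B futility look to come after full accrual if the relevant patient stays on drug for more than 3.5 to 21 months, depending on which of the plan's accrual assumptions applies. The cost is then up to 7 patients, 4.4 on average under the 5% null measured against a design that holds accrual at nine.

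Three stronger conclusions are tempting, and the documents do not support them.

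- A reader might infer that the early-stopping property is certain to be lost. The documents give no time on drug for stable patients, and the calendar footnote could bound it, so the property *may* not be delivered.
- A reader might infer that the error rates are compromised. They are not: alpha is 0.041 with the rule and 0.043 without it. Safety has its own stopping rule in 13.5.1, independent of this look.
- A reader might infer that the Primary Endpoint Completion Date in 13.3.3, "the time the last patient registered has been followed for at least six months after being taken off the study treatment", is part of the same error. It is defined for registry reporting only and governs neither the look nor accrual.

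Cohort A is mostly bounded at four to five cycles. Its approved special-case continuation (7.1.1) has the same open end, but applies only by exception.

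**What to change.** 1. In 13.2.3, trigger the Cohort B interim and final analyses when each of the first 9 (16) evaluable patients has completed the end-of-Cycle-4 response assessment, with any confirmation scan needed, or has stopped treatment earlier. This also settles whether one patient or all nine must qualify.
2. Allow the decision to continue as soon as one centrally read response is on file, since the rule requires only one in nine.
3. In 13.1, define *too rapid* so that accrual pauses if the remaining places would fill before the 9-patient look. On the plan's figures this matters chiefly near 2 per month.

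Aligning the completion date in 13.3.3 is optional.

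The change concerns when data are analysed, not how long anyone is treated. It adds no patients, visits or scans and leaves the design figures (0.041, 0.886, 0.630) as they are. There are two costs. Central reads of the first nine patients must be timely, whereas 6.3.1 describes central reading as retrospective and 13.5.3 raises real-time reading only as a contingency. A short accrual pause is also possible if enrolment is fast and no response has been seen.
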